10.2 Laboratory Data

Laboratory test results for Baseline, Week 12 visits, change from Baseline at Week 12 and change to abnormal status of either below LLN ("Low") or above ULN ("High") from Baseline at Week 12 for all Safety Lab tests (Appendix 6) will be summarized by treatment groups. Shift tables will be used to present change in status (normal to abnormal or abnormal to normal) from Baseline at Week 12. All lab values will be listed and all test values outside the normal range will be flagged. Urinalysis results will be summarized separately for continuous and categorical variables. Pregnancy test results will be listed only.

The pre-dose laboratory test results only within the time window will be considered for analyses safety laboratory data summaries.

For average baseline, it is considered the average of the latest (closest to the target day Day -1) laboratory test result in the screening window (from Day -28 to Day -1) and the pre-dose Day 1 laboratory test result.

For Day 1 value or the latest value prior to the first dose of study drug as baseline, it is considered the laboratory test result in the screening window (from Day -28 to Day -1) not beyond Day -28 laboratory test result.

For screening visit as baseline, it is considered the laboratory test result in the screening window (from Day -28 to Day -1) and the latest laboratory test result.

If the recorded the laboratory test result ($<XX.xx$) is below the lower limit, then the value 0.0 is considered for the laboratory test result.

If the recorded laboratory test result ($>XX.xx$) is above the upper limit, then the value of the ($XX.xx$) is considered for the laboratory test result.

For the purposes of summarization in both the tables and listings, all laboratory values will be converted to standardized units. Reference Covance Lab Manual for schedule of testing.

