**Analysis Populations**

- *Safety Population:* All subjects who receive at least one dose of study medication. Subjects will be included in the treatment group that corresponds to the study medication received during the study.
- *Efficacy Population:* All subjects who receive at least one dose of study medication. Subjects will be included in the randomized treatment group.

- *Pharmacokinetic Population:* All subjects receiving active study medication and having any measurable plasma concentration of study medication at any timepoint.

*Safety Analyses:* Statistical methods for the safety analyses will be primarily descriptive in nature. No formal statistical comparisons of EDP-305 dose levels will be made. Safety data, including adverse events (AEs), vital signs, ECGs, concomitant medications, and laboratory values will be summarized separately for each treatment group. Change from Baseline will be included in summary tables for vital signs, ECG parameters, and laboratory parameters. Shift tables will also be generated for safety laboratory parameters by visit and treatment group. All laboratory data will be included in the data listings and all test values outside the normal range will be flagged. AEs will be summarized by the Medical Dictionary for Regulatory Activities (MedDRA) system organ class and preferred term by treatment group.

*Efficacy Analyses:* Proportion of subjects with at least 20% reduction in ALP from pretreatment value or normalization of ALP at Week 12. Treatment comparisons will be made using a Mantel-Haenszel test comparing each of the active treatment groups to placebo, respectively.

*Pharmacokinetic Analyses:* Plasma PK parameters for each dose level will be calculated from the concentrations of EDP-305 and its major metabolites (as applicable) measured in predose and postdose plasma samples. For each EDP-305 dose level, descriptive statistics (sample size, arithmetic means, geometric means, standard deviation, % coefficient of variation, minimum, median, and maximum) will be presented. Figures will be created to display mean and individual subject EDP-305 concentration time curves in plasma on both a linear and logarithmic scale. The following PK parameters will be calculated as indicated for plasma EDP-305 and its major metabolites:  $AUC_{0-t}$ ,  $C_{max}$ , and  $T_{max}$ .

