### **11.6.2 Clinical Laboratory Data**

Summaries of clinical laboratory results will be performed using an 8-number summary by visit and treatment. All subjects in the safety population will be included in these summaries.

The number and percentage of subjects with treatment-emergent laboratory abnormalities will be summarized by treatment group. In addition, shift from baseline tables will be generated by visit and treatment group.

Change from Baseline will be included in summary tables for laboratory parameters. Shift tables will also be generated for safety laboratory parameters by visit and treatment group. All

laboratory data will be included in the data listings and all test values outside the normal range will be flagged.

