6.3 Study Day Windows

The windows for all visits including PK draws appear in table below:

Visit	Target Day	Time window
Screening	Day -1	Day -28 to Day -1
Day 1	Day 1	N/A
Day 3	Day 3	N/A
Week 2	Day 14	Day 4 to Day 21
Week 4	Day 28	Day 22 to Day 42
Week 8	Day 56	Day 43 to Day 70
Week 12	Day 84	Day 71 to less than or equal to End of Treatment+7 days
Treatment-Free Follow-up Week 4	Day 112	Greater than End of Treatment+7 days to last visit

- Samples at each visit should be obtained at different times postdose relative to each of the other visits (2, 4, and 8)
- The target day for the screening visit is Day -1 during the period of Day -28 to Day -1

The relative day will be computed for each laboratory, vitals, ECG and PD data point. The relative day will be calculated as visit date-date of first dose+1. For data collected prior to first dose, the relative day will be calculated as visit date-date of first dose. When there are multiple observations within a visit window, the value closest to the target day will be analyzed..

PK/PD Draw Timing

Visit	Target Day	PK/PD Substudy (PK, C4, FGF19, BA, and additional ALP samples)	Population	
			For subjects not substudy	
			PK	PD (FGF19, BA, C4)
Day 1	Day 1	At predose and 2, 6, and 8 hr postdose	at predose and two samples postdose; 
 • First sample collected 1 to 3 hours postdose • Second sample at least 1 hour later 	At predose
Week 2	Day 14	at predose and two samples postdose; 
 • First sample collected 1 to 3 hours postdose • Second sample at least 1 hour later 	at predose and two samples postdose; 
 • First sample collected 1 to 3 hours postdose • Second sample at least 1 hour later 	At predose
Week 4	Day 28	at predose and two samples postdose; 
 • First sample collected 1 to 3 hours postdose • Second sample at least 1 hour later 	at predose and two samples postdose; 
 • First sample collected 1 to 3 hours postdose • Second sample at least 1 hour later 	At predose
Week 8	Day 56	at predose and two samples postdose; 
 • First sample collected 1 to 3 hours postdose • Second sample at least 1 hour later 	at predose and two samples postdose; 
 • First sample collected 1 to 3 hours postdose • Second sample at least 1 hour later 	At predose

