10.3 Vital Signs

Vital signs will include heart rate (HR), respiratory rate (RR), blood pressure (BP) and oral temperature. Vital signs results will be summarized by timepoint where it shows change from Baseline, and significant changes in vital signs by treatment. Significant vital signs to be included are:

Pulse Rate

- < 50 bpm
- > 120 bpm
- ≥ 30 bpm increase from Baseline
- ≥ 30 bpm decrease from Baseline

Blood Pressure

- SBP > 150 mmHg or DBP > 100 mmHg
- SBP > 200 mmHg or DBP > 110 mmHg

Respiration Rate

- < 8 breaths/min
- > 40 breaths/min

Temperature

- > 38.3°C
- ≥ 1.1°C increase from Baseline (Baseline > 36.8°C)

Change in Weight

- ≥ 5% increase from Baseline
- ≥ 5% decrease from Baseline

All vital sign results will be listed.

Weight may be collected in kilograms (kg) or pounds (lb) and height may be collected in centimeters (cm) or inches (in). BMI will be reported in kg/m².

For metric measurements kg and cm:

$$\text{BMI} = \text{Weight}/[(\text{Height} \times 100)^2].$$

For English measurements lb and in:

$$\text{BMI} = [\text{Weight}/(\text{Height})^2] \times 703.$$

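### SAP 10.2 tabulates safety laboratory data only at Baseline and Week 12, where the protocol requires by-visit tables and a count of treatment-emergent abnormalities; coagulation has no scheduled Week 12 result.

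*SAP*

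**What the plan says.** **Protocol.** Section 11.6.2 sets three laboratory outputs for the safety population:

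- A descriptive summary: "Summaries of clinical laboratory results will be performed using an 8-number summary by visit and treatment".
- A by-arm count: "The number and percentage of subjects with treatment-emergent laboratory abnormalities will be summarized by treatment group".
- Shift tables by visit and arm. The synopsis asks for the same: "Shift tables will also be generated for safety laboratory parameters by visit and treatment group".

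**SAP 10.2.** The tables are built on one post-baseline visit. The opening sentence covers "Laboratory test results for Baseline, Week 12 visits, change from Baseline at Week 12 and change to abnormal status" for all Appendix 6 tests. The shift sentence reads: "Shift tables will be used to present change in status (normal to abnormal or abnormal to normal) from Baseline at Week 12". A further sentence restricts the data: "The pre-dose laboratory test results only within the time window will be considered for analyses safety laboratory data summaries". There is no count of treatment-emergent abnormalities across visits.

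**Week 12 window.** SAP 6.3 defines it as "Day 71 to less than or equal to End of Treatment+7 days".

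**Other safety data in the same SAP.** Section 10.3 says: "Vital signs results will be summarized by timepoint where it shows change from Baseline". Section 10.5 summarises ECGs by timepoint and also by maximum QTcF and maximum change from baseline.

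**Coagulation.** SAP Appendix 6 lists INR, PT and PTT. The schedules of assessments in both documents mark PT/PTT and INR at Screening and the end-of-study visit only.

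**The concern.** The SAP narrows an analysis that the protocol specifies, and does not say that it has done so or why. Two groups of results drop out of the 10.2 tables: abnormalities that appear and resolve before Week 12, and results from subjects who stop early and so have no value in the Week 12 window. The second group includes anyone stopped for toxicity, whose laboratory values are among those a safety table most needs to show.

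Safety and tolerability is a secondary objective. If 10.2 is followed as written, the tables for the uncovered tests can make an active arm look cleaner than it was. One instruction also cannot be carried out from scheduled data: a Week 12 coagulation table.

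**Working it through.** The plan gives no figure to reproduce here. The check compares the texts and counts visits, days and tests.

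**1. Texts compared**

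| Output | Protocol synopsis and 11.6.2 | SAP 10.2 |
|---|---|---|
| Descriptive summary | Every visit, by arm | Baseline and Week 12, by arm |
| Shift tables | Every visit, by arm | Baseline to Week 12 |
| Abnormalities | Subjects with treatment-emergent abnormalities, tied to no visit | Change to Low or High at Week 12 |

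**2. Visits covered.** Both schedules mark safety laboratory tests after baseline at Day 3, Weeks 2, 4, 8 and 12, and the end-of-study visit (Week 16). That is 6 visits, of which 10.2 tabulates 1. Counting on-treatment visits only, it is 1 of 5.

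**3. Who has no Week 12 window.** The window runs from Day 71 to end of treatment + 7.

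- Treatment ends on Day 84: the window is Day 71 to Day 84 + 7 = 91.
- The window is empty when end of treatment + 7 < 71, so when treatment ends before Day 64. Day 63 gives 63 + 7 = 70.
- An early end-of-treatment visit in these subjects falls in an earlier visit window or in follow-up, and 10.2 tabulates neither.

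**4. How many subjects.** The planned 119 at 3:3:1 gives 51, 51 and 17. The sample-size section plans for 10% discontinuation, so 0.10 × 51 = 5.1 per active arm. The documents do not say when subjects stop, so the timings below are assumptions:

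- No one stops before Day 64: 0 per active arm.
- Stopping is uniform over 84 days: 5.1 × 63/84 = 3.8, about 4.
- Everyone who stops does so before Day 64: about 5.

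**5. Which tests have no by-visit table elsewhere.** SAP Appendix 6 has 26 chemistry lines.

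- 9 have by-visit summaries in SAP 9.1.4 and 9.2: ALP, ALT, AST, GGT, bilirubin, cholesterol, triglycerides, HDL and LDL.
- 1 (ApoE) is reported as a baseline characteristic.
- 26 − 9 − 1 = 16 remain, including creatinine, BUN, electrolytes, CK, amylase, lipase and glucose.
- All 11 haematology lines, the 3 coagulation tests and urinalysis also have none.
- By-visit safety shift tables are missing for every test.

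**6. Coagulation.** The only scheduled post-baseline draw is at end of study, Day 112 ± 2, so Day 110 to 114. The Week 12 window ends on Day 91 when treatment ends on Day 84. Scheduled Week 12 coagulation results: none. Unscheduled draws are possible when raised liver enzymes are followed up under Protocol 10.2.

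**The case against.** The best case against acting has five parts.

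- **The SAP has a procedure for departures.** Its introduction says that changes to protocol analysis methods that are not a principal feature will be described and justified in the study report. That stands as a procedure. But the SAP does not identify this change, and deferring the justification does not remove the conflict.
- **Treatment-emergent is not defined for laboratory data.** This is correct. The protocol ties its count to no visit, so counting any post-baseline occurrence is the natural reading, but it is a reading. The Week 12 change to Low or High is a narrow version of that count. Including unscheduled values is likewise a choice made in the fix, not protocol text.
- **Other parts of the plan give cover.** Section 9 gives by-visit summaries for the main liver tests and lipids. SAP 10.2.1 counts ALT/AST-based events by arm, including an accompanying INR rise. All values are listed and flagged. Protocol 8.3 asks that findings the investigator judges clinically significant be recorded as adverse events. The DSMB sees unblinded data. All this narrows the gap. It does not give by-arm incidence for the remaining tests, because listings are not incidence tables and adverse events depend on the investigator's judgement.
- **Coagulation may not be meant.** The schedule footnote defines safety laboratory tests as chemistry, haematology and urinalysis. But 10.2 applies its tables to all of Appendix 6, which lists coagulation. No scheduled result is lost at Week 12; the instruction simply has no scheduled data behind it.
- **Appendix 4 is not in the supplied text.** Its list of outputs could not be checked. It is cited only for the interim and DSMB outputs, and it would not change the wording of 10.2.

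**Conclusion.** The concern holds. SAP 10.2 conflicts with Protocol 11.6.2 and the synopsis on summaries, shift tables and the abnormality count, and its Week 12 coagulation table has no scheduled data.

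The table coverage, 1 of 6 post-baseline visits, and the list of uncovered tests follow directly from the documents. The number of subjects with an empty Week 12 window, 0 to 5 of 51 per active arm, rests on the planned 10% discontinuation rate and on assumed stopping times.

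The consequence is possible understatement of laboratory abnormalities in the study tables, mainly for tests outside the liver and lipid panels. The primary endpoint and the adverse-event secondary endpoint are not affected. This should be corrected, but it does not threaten the trial's main conclusion.

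**What to change.** Amend SAP 10.2 as follows:

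1. Restore 8-number summaries and shift tables by arm at every scheduled visit, for all Appendix 6 safety tests. Tabulate coagulation from Screening to end of study, matching the schedule.
2. Restore the number and percentage of Safety-population subjects with any treatment-emergent laboratory abnormality, by arm. Define it over all post-baseline results, including early end-of-treatment and unscheduled values.
3. Limit the in-window restriction to the by-visit tables, so that it does not remove values from that count.
4. Optionally, add a shift from baseline to the worst post-baseline value. Neither document specifies this.

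The cost is SAP wording and a few more tables. No new data collection is needed.

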#### 3.1 Subject Inclusion Criteria

Each subject must meet all of the following criteria to be enrolled into this study:

1. An informed consent document must be signed and dated by the subject
2. Male and female subjects of any ethnic origin between the ages of 18 and 75 years, inclusive
3. Male or female with a diagnosis of PBC by at least two of the following criteria:
  - History of ALP above ULN for at least 6 months
  - Positive Anti-Mitochondrial Antibodies (AMA) titers ( $>1/40$  on immunofluorescence or M2 positive by enzyme linked immunosorbent assay [ELISA] or positive PBC-specific antinuclear antibodies [PBC-ANAb])
  - Documented liver biopsy result consistent with PBC (with no cirrhosis)
4. For subjects with no documented liver biopsy performed within 2 years, subjects must undergo a transient elastography (Fibroscan) showing liver stiffness  $<14.0$  kPA
5. Must be on a stable dose of UDCA 12-20 mg/kg/day for at least 6 months prior to Screening or intolerant of UDCA in the opinion of the Investigator (no UDCA for at least 12 weeks prior to Screening)
6. Alkaline Phosphatase (ALP)  $\geq 1.67 \times$  ULN and/or total bilirubin  $>ULN$  but  $<2 \times$  ULN ( $<2.4$  mg/dL)
7. Subjects must have Screening laboratory values for Hepatitis B surface antigen (HBsAg), anti-HCV antibodies and HCV RNA negative, and Human Immunodeficiency Virus (HIV) 1 and 2 antibodies (Ab) as seronegative. NOTE: Subjects previously infected by chronic hepatitis C and treated with direct acting antivirals (DAAs) with sustained virologic response (SVR) for at least 3 years will be allowed.
8. Female subjects of childbearing potential must agree to use two effective methods of contraception from the date of Screening until 90 days after the last dose of EDP-305. Effective methods of contraception are defined as:
  - a condom for the male partner and at least one of the following for the female participant:
    - Intrauterine device
    - Oral, injectable, implantable, transdermal, or intravaginal hormonal contraceptiveNote: The above does not apply to female subjects of non-childbearing potential (ie, physiologically incapable of becoming pregnant) defined as:
  - has had a complete hysterectomy greater than or equal to 3 months prior to dosing or
  - has had a bilateral oophorectomy (ovariectomy) or
  - has had a bilateral tubal ligation or fallopian tube inserts or

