9.1.4 Change from Baseline and Percent Change from Baseline for ALP

A descriptive summary will be provided for ALP values, change from Baseline and percentage change from Baseline using 8-number summary by visit and treatment group.

Change from Baseline and percentage change from Baseline at Week 12 will be analyzed using an ANCOVA model with treatment as fixed effect and the associated baseline value as covariate. Least squares means and standard errors will be presented for each visit, p-value and 2-sided 95% confidence interval for treatment differences will be presented for each visit. Significance tests will be based on least-squares means using a two-sided $\alpha = 0.05$.

A by-subject listing will be provided for observed and derived variables.

Mean \pm SD ALP values and change from baseline by visit and treatment group will be plotted and also separately for the subgroups of UDCA and Fibrates strata. Scatterplots of the percentage change from baseline in ALP at Week 12 against the baseline ALP will also be produced.

Additional ALP endpoints investigated include:

- Decrease in ALP $\geq 10\%$ at 12 weeks
- Decrease in ALP $\geq 15\%$ at 12 weeks
- Decrease in ALP $\geq 20\%$ at 12 weeks
- Decrease in ALP $\geq 40\%$ at 12 weeks
- ALP < ULN and Decrease in ALP $\geq 10\%$ at 12 weeks
- ALP < ULN and Decrease in ALP $\geq 20\%$ at 12 weeks
- ALP < ULN and Decrease in ALP $\geq 40\%$ at 12 weeks
- ALP < 1.67xULN and Decrease in ALP $\geq 10\%$ at 12 weeks
- ALP < 1.67xULN and Decrease in ALP $\geq 20\%$ at 12 weeks
- ALP < 1.67xULN and Decrease in ALP $\geq 40\%$ at 12 weeks
- ALP < 2xULN and Decrease in ALP $\geq 10\%$ at 12 weeks
- ALP < 2xULN and Decrease in ALP $\geq 20\%$ at 12 weeks
- ALP < 2xULN and Decrease in ALP $\geq 40\%$ at 12 weeks
- Proportion of subjects at Week 12 with ALP <ULN, \geq ULN and <1.67xULN, \geq to 1.67xULN and < 2xULN and $\geq 2xULN$

ALP Shifts from baseline endpoints will also be evaluated as follows:

- Baseline ALP category ([1.67xULN,2xULN), [2xULN,3xULN), [3xULN,4xULN), [4xULN,5xULN), and $\geq 5xULN$) shifting to Normal, [1*ULN,1.67xULN), [1.67xULN,2xULN), and $\geq 2xULN$ (baseline categories are data dependent)

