9.2.1.1 Bilirubin

A descriptive summary will be provided for Total, Conjugated and Unconjugated Bilirubin values, change from Baseline and percentage change from Baseline using 8-number summary by visit and treatment group.

Change from Baseline and percentage change from Baseline at Week 12 will be analyzed using an ANCOVA model with treatment as fixed effect and the associated baseline value as covariate. Least squares means and standard errors will be presented for each visit, p-value and 2-sided 95% confidence interval for treatment differences will be presented for each visit. Significance tests will be based on least-squares means using a two-sided $\alpha = 0.05$.

Additional endpoints for Bilirubin will include the following:

- Proportion of subjects at Week 12 with Total Bilirubin <ULN, \geq ULN and <1.5xULN, \geq 1.5xULN and <2xULN and \geq 2xULN.
- Shift in total bilirubin from baseline to Week 12 using the same categories as the endpoint in the previous bullet.

A by-subject listing will be provided for observed and derived variables.

Scatterplots of the change from baseline in total bilirubin versus the baseline total Bilirubin value will be produced.

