10.2.1 Subject Safety Monitoring

Subjects will be monitored throughout the study for the following:

- ALT or AST increase to $>5 \times$ Baseline
- ALT or AST increase $>2 \times$ Baseline AND the increase is accompanied by a concomitant Total Bilirubin increase to $>2 \times$ Baseline OR the INR (prothrombin time / partial thromboplastin time) concomitantly increases from Baseline by >0.2
- Elevated Baseline liver chemistry (AST or ALT elevations $2 \times$ Baseline) will require subjects to be reassessed promptly (within 48–72 hours) with full liver biochemistry and physical exam

- Elevations of ALT/AST accompanied by preferred terms indicating: signs or symptoms of right upper quadrant abdominal pain, anorexia, nausea, vomiting fever, eosinophilia, and/or rash

Incidence of these safety categories will be summarized by treatment group and identified on the listings with laboratory data parameters

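### The planned categorical laboratory tables cannot count worsening of ALP from a baseline of 2×ULN or more, or of GGT from a baseline already above normal

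*SAP*

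**What the plan says.** SAP 10.2 covers the safety laboratory tests in Appendix 6, which include ALP and GGT. It plans values and change from Baseline at Week 12, counts of change to Low or High status, and shift tables: "Shift tables will be used to present change in status (normal to abnormal or abnormal to normal) from Baseline at Week 12".

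SAP 9.1.4 adds an ALP shift table. The baseline side runs "Baseline ALP category ([1.67xULN,2xULN), [2xULN,3xULN), [3xULN,4xULN), [4xULN,5xULN") and then 5×ULN and above. The post-baseline side is "shifting to Normal, [1*ULN,1.67xULN), [1.67xULN,2xULN), and" a last band of 2×ULN and above. Only the baseline categories are called data dependent, so the top post-baseline band is fixed.

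Other liver tests are treated differently. For bilirubin, SAP 9.2.1.1 plans: "Shift in total bilirubin from baseline to Week 12 using the same categories as the endpoint in the previous bullet". Those categories are below ULN, 1 to below 1.5, 1.5 to below 2, and 2×ULN or more. For ALT and AST, SAP 10.2.1 defines rises relative to Baseline, some combined with bilirubin or INR, and says: "Incidence of these safety categories will be summarized by treatment group and identified on the listings with laboratory data parameters". GGT (SAP 9.2.1.4) gets numerical summaries, ANCOVA, a listing and a mean plot, but no categories.

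Protocol 11.6.2 promises shift tables by visit and treatment group, and the number and percentage of subjects with treatment-emergent laboratory abnormalities.

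**The concern.** Protocol 3.1, criterion 6, admits subjects with ALP of at least 1.67×ULN, with total bilirubin between 1 and 2×ULN, or with both. Anyone who enters by the ALP route is abnormal for ALP at baseline. For that subject a normal/abnormal table can show improvement or no change, never worsening. The graded ALP table should close this gap, but its post-baseline side stops where most of its baseline side begins.

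The other categorical ALP outputs in SAP 9.1.4 do not help. They are decreases of at least 10, 15, 20 or 40%, values below a ceiling combined with a decrease, and Week 12 proportions whose top band is again 2×ULN or more. None counts an increase.

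At stake is a per-arm count of biochemical cholestatic worsening, which belongs to the safety objective. The adverse-event route is weak for ALP: Protocol 6.1.1 blinds investigators and site staff to post-baseline ALP, and Protocol 8.3 has investigators judge only unblinded values for clinical significance. The final tables therefore carry more weight for ALP than for most tests.

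**Working it through.** No power or sample-size figure is involved. The check goes through the cells of each planned table and asks, for each baseline row, whether any post-baseline cell proves a move to a higher band.

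**Normal/abnormal table (SAP 10.2).** From a normal baseline, one cell shows worsening. From a baseline above ULN, none does, because high-to-high is a single state. This is the only planned categorical display for GGT. As an illustration, GGT rising from 3 to 6×ULN (6/3 − 1 = +100%) is recorded as abnormal to abnormal.

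**ALP table (SAP 9.1.4), in multiples of ULN.**

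| Baseline band | What the post-baseline cell of 2 or more holds | Does a cell prove worsening? |
|---|---|---|
| 1.67 to <2 | higher values only | yes |
| 2 to <3 | same band and higher | no |
| 3 to <4 | lower, same and higher | no |
| 4 to <5 | lower, same and higher | no |
| 5 or more | lower and same band, with rises inside that band | no |

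So 1 of 5 rows can show worsening. Worked examples, where the Week 12 value always falls in the band of 2×ULN or more:

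- 2.1 to 4.2: 4.2/2.1 − 1 = +100%
- 3.5 to 7.0: 7.0/3.5 − 1 = +100%
- 3.5 to 2.5: 2.5/3.5 − 1 = −28.6%

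The last two share a baseline row, so they share a cell, although one subject doubled and the other meets the 20% reduction criterion. By contrast, 1.8 to 3.6 (also +100%) does show as worsening.

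**Bilirubin table (SAP 9.2.1.1), same method.** From 1 to <1.5 there are two worsening cells, and from 1.5 to <2 there is one. Using the same bands on both axes is what makes this work.

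**ALP with matched bands.** With normal, 1 to <1.67, 1.67 to <2, 2 to <3, 3 to <4, 4 to <5, and 5 or more on both axes, the number of higher cells per row is 6, 5, 4, 3, 2, 1 and 0. Only the top row still lacks one: 5.5 to 11 (11/5.5 − 1 = +100%) stays in its cell. A count of percentage rises covers that case.

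**Timing.** Under SAP 6.3 the Week 12 window opens on Day 71. A subject whose last on-treatment sample is earlier has no Week 12 value and drops out of a Week 12 shift table. The by-visit tables in Protocol 11.6.2 would keep that subject at the visits attended.

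**The case against.** The strongest reply is that the information is not lost. SAP 9.1.4 gives ALP change and percentage change by visit and arm in an 8-number summary. That summary includes the maximum, so the largest rise in each arm is printed. A scatterplot of Week 12 percentage change against baseline ALP shows each subject with a Week 12 value, and by-subject listings are planned. GGT has the same summaries and a listing. The DSMB receives unblinded results during the trial (SAP 12). All of this stands. A reader might infer that worsening in subjects already abnormal at entry cannot be seen at all, or that every laboratory shift table is merely normal versus abnormal. The documents support neither reading.

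It can also be said that the ALP shift table is an efficacy display whose post-baseline bands repeat the response thresholds listed just above it. That explains the design, but no safety table then fills the gap. The responder analysis and the decrease thresholds do separate improved subjects from the rest. What stays merged is unchanged and worse.

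The blinding argument applies to ALP. Protocol 6.1.1 does not list GGT as blinded to sites, so a clinically significant GGT rise can be recorded as an adverse event.

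Protocol 11.6.2 promises counts of treatment-emergent laboratory abnormalities, but SAP 10.2 neither defines nor grades them. Its nearest output, change to Low or High status, cannot be newly met by a subject who is already High. The output list in SAP Appendix 4, cited for the interim and DSMB reports, is not in the text available, so further displays there cannot be judged.

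Finally, a matched ALP table has 7 × 7 = 49 cells, sparse for a placebo arm of 15 planned subjects (17 if 119 are enrolled, 119/7). This is fair, and it is a reason to add the compact counts of percentage rises.

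**Conclusion.** The point holds for the categorical ALP and GGT tables only. Four of the five ALP baseline rows, all those starting at 2×ULN or above, have no cell that proves worsening. GGT has none from a baseline above ULN. Bilirubin is covered by matched bands and ALT/AST by the rises in SAP 10.2.1. ALP worsening from the band 1.67 to below 2×ULN is visible.

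The consequence is limited: no endpoint, estimate, error rate or data collection is affected. Readers would have maxima, plots and listings, but no planned count per arm of subjects whose ALP or GGT rose from an already abnormal level. The finding assumes that the ALP post-baseline bands are applied as written, and that the treatment-emergent abnormality counts promised in the protocol are not defined elsewhere in a way that captures such rises.

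**What to change.** - **ALP (SAP 9.1.4):** use the same bands at baseline and post-baseline: normal, 1 to <1.67, 1.67 to <2, 2 to <3, 3 to <4, 4 to <5, and 5×ULN or more. This also gives a fixed row to bilirubin-route subjects with ALP below 1.67×ULN.
- **GGT (SAP 10.2):** replace the normal/abnormal shift with ULN-multiple bands on both axes.
- **Counts of rises:** for each arm, give the number and percentage of subjects whose ALP or GGT rises from Baseline by prespecified amounts, for example at least 20%, 50% and 100%. Label these as descriptive cut-offs, since the documents supply none. State which baseline definition in SAP 6.2 applies.
- **Timing:** present these tables by visit, as Protocol 11.6.2 promises, so that subjects without a Week 12 value are not lost. In the same edit, define the treatment-emergent abnormality table promised there.
- **ALT and AST:** graded shifts would be consistent but are optional, given SAP 10.2.1.

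The cost is table shells and programming. No new data, design change or alpha adjustment is needed.
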